6.0 STRATIFICATION FACTORS

6.1 Stratification Factors

Stratification factors do not apply to Step 1 Initial Registration or Step 3 Crossover Registration.

6.2 Randomization

Patient will be randomized at Step 2 Randomization using a dynamic balancing algorithm with stratification based on prior treatment with irinotecan: yes vs. no. (38)

7.1 Pre-Medication *

Diphenhydramine (or other H₁-antagonist) 50 mg intravenously, given once 30-60 minutes prior to first dose of cetuximab.

Dexamethasone 10 mg intravenously, given 30-60 minutes prior to irinotecan.

Patients on Arm 1 may receive institutional recommended management for nausea. Patients on Arms 2 and 3 may receive maximum doses of the following drugs:

- ondansetron 8 mg IV,
- dolasetron 12.5 mg IV,
- granisetron 1 mg IV,
- any oral form of 5-HT₃ inhibition.

* NOTE: These may be modified at the discretion of the treating physician.

7.2 Treatment – Arm 1

Patients assigned to Arm 1 will receive the following treatment until meeting one of the criteria in [Section 7.6](#).

Agent	Dose	Route	Day	Schedule *
Cetuximab	500 mg/m ²	IV over 120 min for initial dose and over 60 min for subsequent doses **	1, 15	Prior to irinotecan
Irinotecan	180 mg/m ²	IV over 90 min	1, 15	After cetuximab

* Note: One cycle = 28 days

** Subsequent doses may be given over 60 minutes or 120 minutes at the discretion of the treating physician.

7.3 Treatment – Arm 2

Patients assigned to Arm 2 will receive the following treatment until meeting one of the criteria in [Section 7.6](#).

Agent	Dose	Route	Day	Schedule *
Cetuximab	500 mg/m ²	IV over 120 min for initial dose and over 60 min for subsequent doses ***	1, 15	Prior to irinotecan
Irinotecan	180 mg/m ²	IV over 90 min	1, 15	After cetuximab
Vemurafenib	960 mg (1920 mg total daily dose) **	PO BID	1-28	Daily

* Note: One cycle = 28 days

** Patients should take 4 tablets in the morning and 4 tablets in the evening with or without a meal. A missed dose can be taken up to 4 hours prior to the next dose.

*** Subsequent doses may be given over 60 minutes or 120 minutes at the discretion of the treating physician.

7.4 Drug Compliance Documentation

Drug compliance for vemurafenib will be recorded by patients in an Intake Calendar (see [S1406](#) protocol abstract page on the SWOG website [www.swog.org] for an example). Institutional CRAs will review and ascertain patient adherence with protocol therapy at the end of treatment for each cycle. Calendar should be kept in the patient's clinic chart. Note that the Intake Calendar is provided only as a tool for tracking patient compliance. Sites may utilize institutional pill diaries or other source documentation in place of the Intake Calendar at the discretion of the treating physician.

7.5 Crossover following disease progression on Arm 1

- a. Following radiographic documentation by RECIST 1.1 (in [Section 10.2d](#)) of disease progression, patients initially randomized and treated on Arm 1 may register to Step 3 Crossover Registration to be treated with vemurafenib, irinotecan, and cetuximab per the schedule and doses listed below. Patients must be eligible and registered for Step 3 Crossover Registration per [Section 5.3](#). Patients must be re-staged at time of progression on Arm 1 prior to registration to Step 3 Crossover Registration. Follow-up for these patients after crossover will be the same as those patients initially randomized to Arm 2.

b. Treatment – Arm 3

Patients who are registered to Step 3 Crossover Registration will receive the following treatment until meeting one of the criteria in [Section 7.6](#).

Agent	Dose**	Route	Day	Schedule*
Cetuximab	500 mg/m ²	IV over 60 min	1, 15	Prior to irinotecan
Irinotecan	180 mg/m ²	IV over 90 min	1, 15	After cetuximab
Vemurafenib	960 mg (1920 mg total daily dose)	PO BID	1-28	Daily

* Note: One cycle = 28 days

** If patient was on a reduced dose of cetuximab and/or irinotecan in Arm 1, he or she should begin treatment at that dose in Arm 3.

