Adverse effects reported in > 20% to 100% of subjects treated with cetuximab include: nail changes, radiation recall, rash, itching, dry skin, acne, dehydration, weight loss, anorexia, mucositis, constipation, diarrhea, vomiting, nausea, insomnia, headache, fatigue, pain, fever, infection, cough, and dyspnea.

Adverse effects reported in 4% to 20% of subjects include: allergic reaction/hypersensitivity which may cause rash, hypotension, wheezing, shortness of breath, and swelling of the face or throat, confusion, depression, anxiety, syncope, sepsis, and pulmonary embolism.

Adverse effects that are rare and serious that occurred in 3% or less of subjects include: interstitial lung disease, renal failure, and cardiopulmonary arrest and/or sudden death.

Note: Cetuximab in combination with other agents could cause an exacerbation of any adverse event currently known to be caused by the other agent, or the combination may result in events never previously associated with either agent.

Additional information on common, serious, or severe reactions includes:

Infusion Reactions: In clinical trials, severe, potentially fatal infusion reactions were reported. These events included the rapid onset of airway obstruction (bronchospasm, stridor, and hoarseness), hypotension, shock, loss of consciousness, myocardial infarction, and/or cardiac arrest. Approximately 90% of severe infusion reactions occurred with the first infusion despite premedication with antihistamines.

Dermatologic Toxicity: In clinical studies of cetuximab, dermatologic toxicities, including acneiform rash, skin drying and fissuring, and inflammatory and infectious sequelae (e.g. blepharitis, conjunctivitis, keratitis, cheilitis, cellulitis, cyst), and hypertrichosis were reported. In patients with advanced colorectal cancer, acneiform rash was reported in 88% (560/633) of all treated patients, and was severe (Grade 3 or 4) in 12% (79/633) of these patients. Subsequent to the development of severe dermatologic toxicities, complications including *S. aureus* sepsis and abscesses requiring incision and drainage were reported.

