8.2 General Considerations

- a. Where several toxicities with different grades or severity occur at the same time, the dose modification applied should be the greatest reduction applicable.
- b. The maximum dose delay for any reason is 3 weeks.
- c. Doses omitted during a cycle will not be made up.
- d. If treating investigator feels an event is attributable to another drug, then, after conversation with the Study Chair, other modification may be considered.
- e. Patient may continue protocol treatment if either cetuximab or irinotecan must be stopped. If patient must stop vemurafenib treatment, patient should be removed from all protocol treatment.
- f. Advise patients to avoid sun exposure while on treatment with vemurafenib and cetuximab. Encourage patients to wear protective clothing and to use a broad spectrum UVA/UVB sunscreen and lip balm (SPF \geq 30) when outdoors.

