3 or 4	At the first occurrence of rash, hold cetuximab until recovery to Grade \leq 2. If there is improvement in the rash upon holding therapy, Then resume at same dose. At second occurrence of rash, hold cetuximab until recovery to Grade \leq 2. If there is improvement in the rash upon holding therapy, reduce cetuximab by one dose level and resume. At third occurrence, remove patient from cetuximab treatment.	At the first occurrence of rash, hold cetuximab until recovery until recovery to Grade \leq 2. If there is improvement in the rash upon holding therapy, then resume at same dose. At second occurrence of rash, hold cetuximab and vemurafenib until recovery to Grade \leq 2. If there is improvement in the rash upon holding therapy, reduce cetuximab by one dose level and resume. At third occurrence, hold cetuximab and vemurafenib until recovery to Grade \leq 2 If there is improvement in the rash upon holding therapy, reduce vemurafenib and resume. At fourth occurrence, the patient must be removed from protocol treatment.

CLOSED EFFECTIVE 04/01/2016

I. Photosensitivity

Toxicity Grade	Dose Modification
3 or 4	Hold all treatment until recovery to \leq Grade 1. Reduce vemurafenib by one dose level.

m. Uveitis

Toxicity Grade	Dose Modification
2	Hold vemurafenib until recovery to \leq Grade 1. Resume at same dose level.
3 or 4	Hold vemurafenib until recovery to \leq Grade 1. Reduce vemurafenib by one dose level.

n. Hypersensitivity Reaction*, Cytokine Release*, Infusion Reaction

Toxicity Grade	Dose Modification
1	Decrease cetuximab infusion rate by 50% until symptoms resolve, then resume at the initial planned rate.
2	Stop cetuximab infusion. Administer H ₁ and/or H ₂ blockers, and/or steroids according to institutional policy. Restart the infusion at 50% lower rate when symptoms resolve and pretreat before all subsequent doses. All subsequent cetuximab doses should be administered at the lower infusion rate.
3 or 4	Stop the infusion. Discontinue cetuximab treatment.

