Toxicity Grade	Dose Modification
1 or 2	Supplementation with magnesium. Closely monitor patient for appropriate magnesium levels.
3 or 4	Institute maximal medical management with magnesium. If Grade \geq 3 persists despite magnesium supplementation, reduce cetuximab by one dose level. At second occurrence, discontinue cetuximab therapy.

r. Other non-hematologic toxicities

Toxicity Grade	Dose Modification
3 or 4	Hold all treatment and monitor toxicity at least weekly. If toxicity resolves to \leq Grade 1 within 3 weeks, reduce irinotecan by one dose level and resume treatment.

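### Section 7.5b carries only reduced doses from Arm 1 into Arm 3; for cetuximab stopped or permanently slowed after a reaction, its table read literally conflicts with 8.3n

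*Combined protocol and SAP*

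**What the plan says.** Section 7.5a says that patients who progress on Arm 1 may register to Step 3 and be "treated with vemurafenib, irinotecan, and cetuximab per the schedule and doses listed below". The 7.5b table lists cetuximab 500 mg/m² on days 1 and 15 over 60 minutes. Its dose footnote reads "If patient was on a reduced dose of cetuximab and/or irinotecan in Arm 1, he or she should begin treatment at that dose in Arm" (meaning the crossover arm). The footnote in 7.2 and 7.3 that leaves later infusions at 60 or 120 minutes to the physician is absent from 7.5b.

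Section 8.3n governs cetuximab reactions and is not limited to an arm:
- Grade 1: the rate is halved temporarily and then returns to plan.
- Grade 2: the infusion restarts at half rate, pretreatment precedes each later dose, and "All subsequent cetuximab doses should be administered at the lower infusion rate".
- Grade 3 or 4: "Stop the infusion. Discontinue cetuximab treatment".

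Two other rules can end cetuximab on Arm 1. For rash (8.3k, Arm 1 column): "At third occurrence, remove patient from cetuximab treatment". For hypomagnesemia (8.3q): "At second occurrence, discontinue cetuximab therapy".

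Section 8.2e adds: "Patient may continue protocol treatment if either cetuximab or irinotecan must be stopped". Section 5.3 sets the Step 3 criteria: progression on Arm 1, a 28-day window, performance status, and marrow, liver and kidney function. None of them concerns a stopped drug or an earlier reaction.

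**The concern.** The footnote in 7.5b anticipates one kind of Arm 1 change, a lower dose. Section 8.3 produces two others: a drug that has ended, and an infusion rate lowered for good. A site that follows the Arm 3 table to the letter would give cetuximab to a patient in whom 8.3n had ended it, or give it faster than 8.3n allows.

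The main stake is safety. Section 3.1c describes severe infusion reactions as potentially fatal and adds: "Approximately 90% of severe infusion reactions occurred with the first infusion despite premedication with antihistamines". For a crossover patient the first infusion was on Arm 1, so the patients most likely to be affected are already identified when they reach Step 3.

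A smaller stake is interpretation. Objective 1.3c asks for OS, response and PFS on Arm 3, and section 11.3 summarises these descriptively without separating patients by the drugs they started. If sites resolve the conflict differently, the summary covers different regimens.

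**Working it through.** The plan states no figure on this point to reproduce. The check is a cross-reading plus simple arithmetic on infusion rates.

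**Step 1. Can the patient exist?** Take an Arm 1 patient with a Grade 3 or 4 reaction. 8.3n ends cetuximab. 8.2e lets the patient stay on protocol treatment with irinotecan. At RECIST progression the patient can meet every item of 5.3. A Grade 2 patient, who stays on slowed cetuximab, reaches Step 3 the same way.

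**Step 2. Rule against table, by Arm 1 event.**

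| Arm 1 event | What 8.3 sets | What 7.5b lists, read literally |
|---|---|---|
| 8.3n Grade 1 | Return to planned rate | No conflict |
| 8.3n Grade 2 | Half rate and pretreatment for all later doses | 60 minutes |
| 8.3n Grade 3–4, no earlier reduction | Cetuximab ended | 500 mg/m² over 60 minutes |
| 8.3q second occurrence | Cetuximab ended | 500 mg/m² if never reduced; 375 if the first episode led to one reduction from 500 |
| 8.3k third rash (Arm 1 column) | Cetuximab ended, after a reduction at the second rash | A reduced dose, 375 mg/m² or lower |

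For rash there is a further uncertainty. The column for Arms 2 and 3 has its own sequence, which starts again at a first occurrence. It does not say whether Arm 1 occurrences count, and it has no step that removes cetuximab alone.

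The footnote is equally silent on irinotecan stopped on Arm 1.

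**Step 3. Size of the rate conflict.** Rate = dose / time.
- Arm 3 table: 500 / 60 = 8.33 mg/m²/min.
- Reaction during a 60-minute infusion: 8.33 / 2 = 4.17 mg/m²/min, which takes 120 minutes. Ratio 8.33 / 4.17 = 2.
- Reaction during a 120-minute infusion: 500 / 120 = 4.17; halved, 2.08 mg/m²/min, which takes 240 minutes. Ratio 8.33 / 2.08 = 4.

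At 375 mg/m² the Arm 3 rate is 375 / 60 = 6.25, against 3.12 or 1.56. At 250 mg/m² it is 4.17, against 2.08 or 1.04. The ratios are again 2 and 4, provided the reaction occurred at that same dose.

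**Step 4. Number of patients.**
- Section 11.1 plans 105 randomized patients, so Arm 1 has about 105 / 2 = 52.5.
- Section 3.1c places allergic or hypersensitivity reactions in its 4% to 20% band: 52.5 × 0.04 = 2.1 and 52.5 × 0.20 = 10.5.
- The documents give no crossover fraction. Assuming one half: 1.05 to 5.25, or about 1 to 5. If every such patient crossed over, it would be about 2 to 10.

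The band is not split by grade and includes Grade 1 reactions, which create no conflict, so these counts lean high. They do not include cetuximab stopped for rash or hypomagnesemia, for which no usable rate of stopping is given.

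**The case against.** The strongest reply is that the section 7 tables give default regimens and section 8.3 modifies them. 8.3n is not tied to an arm, its wording about later doses reads naturally into Arm 3, and the rash table shows that 8.3 applies to Arm 3. The Revision 1 log explains the 60-minute entry: crossover patients would not be receiving cetuximab for the first time. Nothing there suggests an intention to override 8.3n. Sections 7.2 and 7.3 likewise list only 60 or 120 minutes for later doses, although a Grade 2 reaction during the first infusion implies 240.

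Much of this stands. A careful site could apply 8.3n on Arm 3 without being told, so part of the problem is silence rather than opposite instructions. But no statement was found that 8.3 prevails at crossover, and 7.5b is the one place that says what carries over, and it names only a reduced dose. Reading zero as a reduced dose would ease the stopped-drug cases, but zero is not a level in 8.3a, and the rate would still not be covered.

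A reader might also infer more than the text supports:
- *Every stopped patient is scheduled for 500 mg/m².* Not for rash, where a reduction precedes removal, and for hypomagnesemia only if no reduction came first.
- *Section 7.1 contradicts the pretreatment rule because it premedicates only the first cetuximab dose.* A note in 7.1 lets the treating physician modify premedication.
- *The regimens on Arm 3 cannot be told apart.* Section 14.4f requires a Treatment Form after every cycle, including on the crossover arm.
- *The trial's main result is at risk.* Primary PFS in 10.5a runs to first progression or death, before Step 3 treatment. Arm 3 outcomes fall under other objectives, and 8.2e already allows regimens without cetuximab or without irinotecan.

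**Conclusion.** The point holds for the two 8.3n routes. Read literally, 7.5b schedules cetuximab 500 mg/m² over 60 minutes for a patient in whom a Grade 3 or 4 reaction had ended it with no earlier reduction. It also schedules a Grade 2 patient at 2 to 4 times the rate that 8.3n sets for all later doses. The 8.3q route is secondary: the conflict there is that cetuximab restarts at all, whatever the dose. For 8.3k the documents show an unclear carry-over between two rash sequences, not a direct contradiction.

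The conclusion rests on a literal reading of 7.5b and on the absence of a precedence statement. The figure of about 1 to 5 patients should be taken as an upper-side range, not an estimate, because it uses an ungraded frequency and an assumed crossover of one half. Even one such patient would warrant a correction, because the event concerned can be severe and the repair is only wording.

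**What to change.** Reconcile 7.5b (the infusion-time cell and the footnote) and 5.3 with 8.2e, 8.3n, 8.3q and 8.3k. The revised text should state:
- how a discontinued drug, a lowered infusion rate and added pretreatment from Arm 1 apply at the start of Arm 3, for cetuximab and, where relevant, irinotecan;
- whether rash occurrences on Arm 1 count in the sequence for Arms 2 and 3;
- whether a patient who stopped cetuximab or irinotecan on Arm 1 may register to Step 3.

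Which rule applies is for the clinical team; this review proposes none.

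The cost is an extended footnote and a line in 5.3, with no added patients, visits or procedures. As an optional reporting step, the Arm 3 summary could give the number of patients who started each combination of drugs, taken from the Treatment Forms already collected.

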7.6 Criteria for Removal from Protocol Treatment

- Progression of disease or symptomatic deterioration (as defined in [Section 10.2](#)).
- Arm 1 only: If patient progresses per RECIST 1.1 (see [Section 10.2d](#)), patient has the option to crossover to treatment Arm 3.
- Unacceptable toxicity.
- Treatment delay for any reason > 3 weeks.
- The patient may withdraw from the study at any time for any reason.

7.7 Discontinuation of Treatment

All reasons for discontinuation of treatment must be documented in the Off Treatment Notice.

7.8 Follow-Up Period

All patients will be followed until death or 3 years after Step 2 Randomization, whichever occurs first.

8.0 TOXICITIES TO BE MONITORED AND DOSE MODIFICATIONS

8.1 NCI Common Terminology Criteria for Adverse Events

This study will utilize the CTCAE (NCI Common Terminology Criteria for Adverse Events) Version 4.0 for toxicity and Serious Adverse Event reporting. A copy of the CTCAE Version 4.0 can be downloaded from the CTEP home page (<http://ctep.cancer.gov>). All appropriate treatment areas should have access to a copy of the CTCAE Version 4.0.

8.2 General Considerations

- a. Where several toxicities with different grades or severity occur at the same time, the dose modification applied should be the greatest reduction applicable.
- b. The maximum dose delay for any reason is 3 weeks.
- c. Doses omitted during a cycle will not be made up.
- d. If treating investigator feels an event is attributable to another drug, then, after conversation with the Study Chair, other modification may be considered.
- e. Patient may continue protocol treatment if either cetuximab or irinotecan must be stopped. If patient must stop vemurafenib treatment, patient should be removed from all protocol treatment.
- f. Advise patients to avoid sun exposure while on treatment with vemurafenib and cetuximab. Encourage patients to wear protective clothing and to use a broad spectrum UVA/UVB sunscreen and lip balm (SPF \geq 30) when outdoors.

8.3 Dose Modifications

- a. Dose Levels for Treatment Modifications

Agent	Starting Dose	Level -1	Level -2	Level -3
Vemurafenib	960 mg PO BID (total daily dose 1920 mg)	720 mg PO BID (total daily dose 1440 mg)	480 mg PO BID (total daily dose 960 mg)	N/A
Irinotecan	180 mg/m ²	150 mg/m ²	125 mg/m ²	100 mg/m ²
Cetuximab	500 mg/m ²	375 mg/m ²	250 mg/m ²	N/A

* Patients who require dose reductions below the values listed above will be removed from protocol treatment.

- b. Nausea and/or vomiting despite optimal medical management

Institute the recommended management at first occurrence, if reoccurs despite optimal medical management, follow dose modification guidelines below. Recommended management for patients receiving vemurafenib may include maximum doses of the following drugs: ondansetron 8 mg IV, dolasetron 12.5 mg IV, and granisetron 1 mg IV; oral 5-Ht₃ antagonist drugs can be used. If symptoms do not improve, then other alternatives like aprepitant, prochlorperazine, or metoclopramide may be considered. If patient is taking vemurafenib and vomits after taking dose, do not redose vemurafenib.

Patients not receiving vemurafenib should be managed per standard practice.

Toxicity Grade	Dose Modification Arm 1	Arm 2
2	Hold all treatment until recovery to \leq Grade 1. Resume at same dose level.	Hold all treatment until Recovery to \leq Grade 1. Resume at same dose level.
3 or 4	Hold all treatment until recovery to \leq Grade 1. Reduce irinotecan by one dose level.	Hold all treatment until recovery to \leq Grade 1. At the first occurrence, reduce irinotecan by one dose level. At second occurrence, reduce vemurafenib by one dose level. At third occurrence, reduce irinotecan by one dose level. After the fourth occurrence, the patient must be removed from protocol treatment.

c. Diarrhea despite optimal medical management

Recommended management: Loperamide 4 mg at first onset, followed by 2 mg with each loose movement until diarrhea-free for 12 hours (maximum dosage: 16 mg/24 hours).

Toxicity Grade	Dose Modification
2	Hold irinotecan until recovery to \leq Grade 1. Resume at same dose level.
3 or 4	Hold irinotecan until recovery to \leq Grade 1. Reduce irinotecan by one dose level.

d. Neutropenia

Toxicity Grade	Dose Modification
2	Hold irinotecan until recovery to \leq Grade 1. Resume at same dose level.
3 or 4	Hold all treatment until recovery to \leq Grade 1. Reduce irinotecan by one dose level. Use of G-CSF (or PEGylated G-CSF) may be considered.*

* G-CSF or pegylated G-CSF may be utilized per ASCO guidelines (<http://jop.ascopubs.org/cgi/content/full/2/4/196>).

e. Thrombocytopenia

Toxicity Grade	Dose Modification
2	Hold irinotecan until recovery to \leq Grade 1. Resume at same dose level.
3 or 4	Hold all treatment until recovery to \leq Grade 1. Reduce irinotecan by one dose level.

f. Blood Bilirubin Increased

Toxicity Grade	Dose Modification
2	Hold irinotecan until recovery to \leq Grade 1. Resume at same dose level.
3 or 4	Hold irinotecan and vemurafenib until recovery to \leq Grade 1. Reduce irinotecan and vemurafenib each by one dose level.

g. Mucositis

Toxicity Grade	Dose Modification
2	Hold irinotecan until recovery to \leq Grade 1. Resume at same dose level.
3 or 4	Hold all treatment until recovery to \leq Grade 1. Reduce irinotecan by one dose level.

h. Fatigue

Toxicity Grade	Dose Modification	
	Arm 1	Arm 2
2	Hold all treatment until recovery to \leq Grade 1. Resume at same dose level.	Hold all treatment until recovery to \leq Grade 1. Resume at same dose level.
3 or 4	Hold all treatment until recovery to \leq Grade 1. Reduce irinotecan by one dose level.	Hold all treatment until recovery to \leq Grade 1. At the first occurrence, reduce irinotecan by one dose level. At the second occurrence, reduce vemurafenib by one dose level. At third occurrence, reduce irinotecan by one dose level. At the fourth occurrence, the patient must be removed from protocol treatment.

i. Arthralgia

Toxicity Grade	Vemurafenib Dose Modification
2	Hold vemurafenib until recovery to \leq Grade 1. Resume at same dose level.
3 or 4	Hold vemurafenib until recovery to \leq Grade 1. Reduce vemurafenib by one dose level.

j. Pneumonitis

Toxicity Grade	Cetuximab Dose Modification
2	Hold cetuximab until recovery to \leq Grade 1. Resume at same dose level.
3 or 4	Hold cetuximab until recovery to \leq Grade 1 and interstitial lung disease has been ruled out. Reduce cetuximab by one dose level. Discontinue protocol treatment if interstitial lung disease is confirmed by CT scan.

k. Rash

Toxicity Grade	Dose Modification	
	Arm 1	Arm 2 + Arm 3
3 or 4	At the first occurrence of rash, hold cetuximab until recovery to Grade \leq 2. If there is improvement in the rash upon holding therapy, Then resume at same dose. At second occurrence of rash, hold cetuximab until recovery to Grade \leq 2. If there is improvement in the rash upon holding therapy, reduce cetuximab by one dose level and resume. At third occurrence, remove patient from cetuximab treatment.	At the first occurrence of rash, hold cetuximab until recovery until recovery to Grade \leq 2. If there is improvement in the rash upon holding therapy, then resume at same dose. At second occurrence of rash, hold cetuximab and vemurafenib until recovery to Grade \leq 2. If there is improvement in the rash upon holding therapy, reduce cetuximab by one dose level and resume. At third occurrence, hold cetuximab and vemurafenib until recovery to Grade \leq 2 If there is improvement in the rash upon holding therapy, reduce vemurafenib and resume. At fourth occurrence, the patient must be removed from protocol treatment.

CLOSED EFFECTIVE 04/01/2016

I. Photosensitivity

Toxicity Grade	Dose Modification
3 or 4	Hold all treatment until recovery to \leq Grade 1. Reduce vemurafenib by one dose level.

m. Uveitis

Toxicity Grade	Dose Modification
2	Hold vemurafenib until recovery to \leq Grade 1. Resume at same dose level.
3 or 4	Hold vemurafenib until recovery to \leq Grade 1. Reduce vemurafenib by one dose level.

n. Hypersensitivity Reaction*, Cytokine Release*, Infusion Reaction

Toxicity Grade	Dose Modification
1	Decrease cetuximab infusion rate by 50% until symptoms resolve, then resume at the initial planned rate.
2	Stop cetuximab infusion. Administer H ₁ and/or H ₂ blockers, and/or steroids according to institutional policy. Restart the infusion at 50% lower rate when symptoms resolve and pretreat before all subsequent doses. All subsequent cetuximab doses should be administered at the lower infusion rate.
3 or 4	Stop the infusion. Discontinue cetuximab treatment.

* For reporting these events: NCI CTCAE 4.0 defines these reactions differently: "Cytokine release syndromes/acute infusion reactions are different from allergic/hypersensitivity reactions, although some of the manifestations are common to both AEs. An acute infusion reaction may occur with an agent that causes cytokine release (e.g., monoclonal antibodies or other biological agents). Signs and symptoms usually develop during or shortly after drug infusion and generally resolve completely within 24 hours of completion of infusion." See the "Syndromes" section of the CTCAE version 4.0 for a complete list of signs and symptoms of "Cytokine release syndrome/acute infusion reaction;" and see the "Allergy/Immunology" section for a description of hypersensitivity.

CLOSED EFFECTIVE 04/10/2016

o. Electrocardiogram QT Corrected Interval Prolonged

Toxicity Grade	Dose Modification
3 or 4	Withhold vemurafenib until QTc interval \leq 500 msec and resume therapy at one reduced dose level. Permanently remove from protocol treatment if the QTc remains $>$ 500 msec and increased $>$ 60 msec from pre-treatment values after controlling cardiac risk factors for QT prolongation (e.g., electrolyte imbalances, congestive heart failure, bradyarrhythmias).

p. Development of new keratoacanthomas or squamous cell carcinoma of the skin

All patients receiving vemurafenib are recommended to undergo a dermatologic evaluation and head/neck examination by their treating physician for monitoring of keratoacanthomas and squamous cell carcinomas. This evaluation should be done at baseline and every 2 months on therapy. CT imaging of the chest, which is performed at baseline and every 2 months on treatment for disease assessment, should be evaluated for any findings of concern for non-dermatologic squamous cell carcinomas. These evaluations should continue for 6 months after completion of vemurafenib, if deemed clinically appropriate by the treating physician. Any new skin lesions or head/neck/chest findings must be treated appropriately, as directed by a dermatologist or otolaryngologist as indicated, while receiving therapy on this protocol. Patients who develop keratoacanthomas or new squamous cell carcinomas of the skin while being treated on protocol should be managed by removal of the carcinomas by a dermatologist. If the lesions are unable to be removed due to the number or location, then the patient should be removed from all protocol therapy.

q. Hypomagnesemia

Toxicity Grade	Dose Modification
1 or 2	Supplementation with magnesium. Closely monitor patient for appropriate magnesium levels.
3 or 4	Institute maximal medical management with magnesium. If Grade \geq 3 persists despite magnesium supplementation, reduce cetuximab by one dose level. At second occurrence, discontinue cetuximab therapy.

r. Other non-hematologic toxicities

Toxicity Grade	Dose Modification
3 or 4	Hold all treatment and monitor toxicity at least weekly. If toxicity resolves to \leq Grade 1 within 3 weeks, reduce irinotecan by one dose level and resume treatment.

